8.2. Discontinuation from the Study

In order to minimize the amount of missing data and to enable assessment of study objectives as planned in the study protocol, every attempt will be made to keep patients in the study irrespective of the following:

- · adherence to study drug
- · adherence to visit schedule
- missing assessments
- study drug discontinuation due to AE
- development of comorbidities, and
- development of clinical outcomes.

The circumstances listed above are not valid reasons for discontinuation from the study.

Patients will be discontinued in the following circumstances:

- enrollment in any other clinical study involving an investigational product or enrollment in any other type of medical research judged not to be scientifically or medically compatible with this study
- participation in the study needs to be stopped for medical, safety, regulatory, or other reasons consistent with applicable laws, regulations, and good clinical practice (GCP),
- if a female patient becomes pregnant
- if a patient is diagnosed with T1DM
- patient requests to be withdrawn from the study

Patients who agree to provide information relevant to any study endpoint at the end of the study are not considered to have discontinued from the study.

A patient who withdraws consent and clearly indicates that there will be no further contact of any kind with the site will be considered to have discontinued from the study.

Prior to early study discontinuation, the patient may discontinue study drug and will have end-of-study procedures (ET visit) performed as shown in the Schedule of Activities (Section 2). During the ET visit, the patient will be prescribed an appropriate glucose-lowering regimen and glucose self-monitoring plan. Visit 801 (safety follow-up visit) should be performed approximately 4 weeks after the ET visit as the final study visit.

Patients discontinuing from the study prematurely for any reason should complete adverse event and other safety follow-up per Section 2 (Schedule of Activities), Section 9.2 (Adverse Events), and Section 9.4 (Safety) of this protocol.

8.3. Lost to Follow-Up

A patient will be considered lost to follow-up if he or she repeatedly fails to return for scheduled visits and is unable to be contacted by the study site. Every attempt will be made to minimize the number of patients considered lost to follow-up at the end of the study. Patients will be informed about the importance of completing the study and providing updated contact information to the study site when necessary.

9. Study Assessments and Procedures

Section 2 lists the Schedule of Activities, with the study procedures and their timing (including tolerance limits for timing).

Appendix 2 lists the laboratory tests that will be performed for this study.

Unless otherwise stated in the subsections below, all samples collected for specified laboratory tests will be destroyed within 60 days of receipt of confirmed test results. Certain samples may be retained for a longer period, if necessary, to comply with applicable laws, regulations, or laboratory certification standards.

9.1. Efficacy Assessments

9.1.1. Primary Efficacy Assessments

The primary efficacy measurement in this study is mean change in HbA1c values from baseline to 40 weeks, as determined by the central laboratory. Blood samples for HbA1c measurements will be collected at specific clinic visits as summarized in the Study Schedule, Section 2.

9.1.2. Secondary Efficacy Assessments

The following secondary efficacy measures will be assessed at 40 weeks based on data collected at the times shown in the Study Schedule (see Section 2).

- Mean change in body weight
- Proportion of patients achieving a target HbA1c <7% (53 mmol/mol), ≤6.5% (48 mmol/mol), or <5.7% (39 mmol/mol)
- Mean change in fasting serum glucose (FSG) values measured in the central laboratory
- Mean change in daily average 7-point SMBG profiles
- Proportion of patients who achieved weight loss ≥5%, ≥10%, and ≥15%
- Change in daily mean insulin glargine dose

9.1.3. Exploratory Assessments and Procedures

The following secondary efficacy measures will be assessed based on data collected at the times shown in the Study Schedule (see Section 2).

- Mean change in waist circumference
- Changes from baseline in mean BMI
- Mean change in lipids (total cholesterol, high-density lipoprotein, low-density lipoprotein, very low-density lipoprotein, and triglycerides)
- Biomarkers
- APPADL scores
- IW-SP scores
- DTSQs/DTSQc
- EO-5D-5L scores

9.1.4. Appropriateness of Assessments

Efficacy and safety assessments included in this study are generally regarded as reliable and accurate with respect to the efficacy and safety assessments in individuals and populations with T2DM.

9.2. Adverse Events

Investigators are responsible for monitoring the safety of patients who have entered this study and for alerting Lilly or its designee to any event that seems unusual, even if this event may be considered an unanticipated benefit to the patient.

The investigator is responsible for the appropriate medical care of patients during the study.

Investigators must document their review of each laboratory safety report.

The investigator remains responsible for following, through an appropriate health care option, AEs that are serious or otherwise medically important, considered related to the investigational product or the study, or that caused the to discontinue the investigational product before completing the study. The patient should be followed until the event resolves, stabilizes with appropriate diagnostic evaluation. The frequency of follow-up evaluations of the AE is left to the discretion of the investigator.

Lack of drug effect is not an AE in clinical studies, because the purpose of the clinical study is to establish treatment effect.

After the informed consent form (ICF) is signed, study site personnel will record via electronic case report form (eCRF) the occurrence and nature of each patient's preexisting conditions, including clinically significant signs and symptoms of the disease under treatment in the study. In addition, site personnel will record any change in the condition(s) and any new conditions as AEs. Investigators should record their assessment of the potential relatedness of each AE to protocol procedure, investigational product, via eCRF.

The investigator will interpret and document whether or not an AE has a reasonable possibility of being related to study treatment, study device, or a study procedure, taking into account the disease, concomitant treatment or pathologies.

A "reasonable possibility" means that there is a cause and effect relationship between the investigational product, study device and/or study procedure and the AE.

The investigator answers yes/no when making this assessment.

Planned surgeries and nonsurgical interventions should not be reported as AEs unless the underlying medical condition has worsened during the course of the study.

If a patient's investigational product is discontinued as a result of an AE, study site personnel must report this to Lilly or its designee via eCRF, clarifying if possible, the circumstances leading to any dosage modifications, or discontinuations of treatment.

9.2.1. Serious Adverse Events

An SAE is any AE from this study that results in one of the following outcomes:

- death
- initial or prolonged inpatient hospitalization
- a life-threatening experience (that is, immediate risk of dying)
- persistent or significant disability/incapacity
- · congenital anomaly/birth defect
- important medical events that may not be immediately life-threatening or result in
 death or hospitalization but may jeopardize the patient or may require intervention
 to prevent one of the other outcomes listed in the definition above. Examples of
 such medical events include allergic bronchospasm requiring intensive treatment
 in an emergency room or at home, blood dyscrasias or convulsions that do not
 result in inpatient hospitalization, or the development of drug dependency or drug
 abuse.

All AEs occurring after signing the ICF are recorded in the eCRF and assessed for serious criteria. The SAE reporting to the sponsor begins after the patient has signed the ICF and has received investigational product. However, if an SAE occurs after signing the ICF, but prior to receiving investigational product, the SAE should be reported to the sponsor as per SAE reporting requirements and timelines (see Section 9.2) if it is considered reasonably possibly related to study procedure.

Study site personnel must alert Lilly or its designee of any SAE within 24 hours of investigator awareness of the event via a sponsor-approved method. If alerts are issued via telephone, they are to be immediately followed with official notification on study-specific SAE forms. This 24-hour notification requirement refers to the initial SAE information and all follow-up SAE information. Patients with a serious hepatic adverse event should have additional data collected using the eCRF.

Pregnancy (during maternal or paternal exposure to investigational product) does not meet the definition of an AE. However, to fulfill regulatory requirements any pregnancy should be reported following the SAE process to collect data on the outcome for both mother and fetus.

Investigators are not obligated to actively seek AEs or SAEs in subjects once they have discontinued and/or completed the study (the patient disposition case report form (CRF) has been completed). However, if the investigator learns of any SAE, including a death, at any time after a subject has been discharged from the study, and he or she considers that the event reasonably possibly related to the study treatment or study participation, the investigator must promptly notify Lilly.

9.2.1.1. Suspected Unexpected Serious Adverse Reactions

Suspected unexpected serious adverse reactions (SUSARs) are serious events that are not listed in the IB and that the investigator identifies as related to investigational product or procedure. United States 21 CFR 312.32 and European Union Clinical Trial Directive 2001/20/EC and the associated detailed guidances or national regulatory requirements in participating countries require the reporting of SUSARs. Lilly has procedures that will be followed for the identification, recording and expedited reporting of SUSARs that are consistent with global regulations and the associated detailed guidances.

9.2.2. Adverse Events of Special Interest

9.2.2.1. Hypoglycemia

Patients will collect information on episodes of hypoglycemia starting from Visit 2 until the last study visit (Follow-up Visit or Early Termination Visit). For that purpose, patients will be trained about signs and symptoms of hypoglycemia, how to treat hypoglycemia, and how to collect appropriate information for each episode of hypoglycemia in the study according to the Schedule of Activities. Site personnel will enter this information into the eCRF at each visit.

Investigators should use the following definitions and criteria when diagnosing and categorizing an episode considered to be related to hypoglycemia (the plasma glucose [PG] values in this section refer to values determined by a laboratory or International Federation of Clinical Chemistry and Laboratory Medicine plasma-equivalent glucose meters and strips) (ADA 2017, ADA 2018):

Glucose Alert Value (Level 1):

- **Documented symptomatic hypoglycemia** is defined as any time a patient feels that he or she is experiencing symptoms and/or signs associated with hypoglycemia, and has a PG level of ≤70 mg/dL (≤3.9 mmol/L).
- **Documented asymptomatic hypoglycemia** is defined as any event not accompanied by typical symptoms of hypoglycemia, but with a measured PG \leq 70 mg/dL (\leq 3.9 mmol/L).
- **Documented unspecified hypoglycemia** is defined as any event with no information about symptoms of hypoglycemia available, but with a measured PG \leq 70 mg/dL (\leq 3.9 mmol/L).

Clinically Significant Hypoglycemia (Level 2):

- **Documented symptomatic hypoglycemia** is defined as any time a patient feels that he/she is experiencing symptoms and/or signs associated with hypoglycemia, and has a PG level of <54 mg/dL (<3.0 mmol/L).
- **Documented asymptomatic hypoglycemia** is defined as any event not accompanied by typical symptoms of hypoglycemia, but with a measured PG <54 mg/dL (<3.0 mmol/L).

 Documented unspecified hypoglycemia is defined as any event with no information about symptoms of hypoglycemia available, but with a measured PG <54 mg/dL (<3.0 mmol/L).

Severe hypoglycemia (Level 3):

 Severe hypoglycemia is defined as an episode with severe cognitive impairment requiring the assistance of another person to actively administer carbohydrate, glucagon, or other resuscitative actions. These episodes may be associated with sufficient neuroglycopenia to induce seizure or coma. Blood glucose measurements may not be available during such an event, but neurological recovery attributable to the restoration of BG to normal is considered sufficient evidence that the event was induced by a low BG concentration.

Other hypoglycemia categories:

 Nocturnal hypoglycemia is defined as any hypoglycemic event that occurs between bedtime and waking.

If a hypoglycemic event meets the criteria of severe, it needs to be recorded as serious on the AE CRF and reported to Lilly as an SAE.

To avoid duplicate reporting, all consecutive BG values ≤70 mg/dL (3.9 mmol/L) occurring within a 1-hour period may be considered to be a single hypoglycemic event (Weinberg et al. 2010; Danne et al. 2013).

In each case of suspected or confirmed hypoglycemia, it is important that the event be properly categorized, the effect of the intervention be assessed, and the frequency of hypoglycemia be evaluated. The role of dietary changes and physical exercise (or any other contributing factor) in the development of an event should be established. The patient should receive additional education, if deemed appropriate.

9.2.2.2. Severe, Persistent Hyperglycemia

Severe, persistent hyperglycemia will be collected during the trial to assess the risk of extreme imbalance in glycemic control.

Investigators will be trained on the application of criteria for deciding when and how to intervene with patients who do not reach glycemic targets. An additional therapeutic intervention should be considered in patients who develop severe, persistent hyperglycemia after randomization at the discretion of investigator in accordance with American Diabetes Association/European Association for the Study of Diabetes guidance (Inzucchi et al. 2015). Rescue medication will be prescribed as add-on to randomized treatment, and patients will continue to follow the protocol-specified visit schedule.

Because insulin glargine dose adjustments without restrictions will be initiated at the end of the stabilization period (see Section 5.1), decision on the presence of severe, persistent hyperglycemia can be first considered 12 weeks after the initiation of this period (approximately 16 weeks after randomization)...

Add-on glycemic rescue therapy will be allowed for patients who met any one of the following prespecified criteria for severe, persistent hyperglycemia and no intercurrent cause of the hyperglycemia could be identified (investigators should first confirm that the patient is fully compliant with the assigned therapeutic regimen and that the patient does not have an acute condition causing severe hyperglycemia):

- (a) average daily BG from the once-weekly 4-point SMBG profile >270 mg/dL (>15.0 mmol/L) over at least a consecutive 2-week period at any time 16 to 24 weeks post randomization;

 OR
- (b) average daily BG from the once-weekly 4-point SMBG profile >240 mg/dL (>13.3 mmol/L) over a consecutive 2-week period at any time 25 to 32 weeks post randomization;

 OR
- (c) average daily BG from the once-weekly 4-point SMBG profile >200 mg/dL (>11.1 mmol/L) over a consecutive 2-week period at any time beyond the first 32 weeks post randomization.

 OR
- (d) HbA1c ≥8.5% at 24 weeks, with inadequate response to the existing regimen defined as improvement in HbA1c over the last 3 months (Week 12 to Week 24) that is, <0.3%

Rescue therapy option:

The criteria described above for severe, persistent hyperglycemia will only be applicable after Week 16. The first choice before initiating any rescue therapy for those patients during the initial 16 weeks will be to follow the TTT algorithm to increase the dose of insulin glargine.

Rescue treatment with pramlintide, DPP-4 inhibitors, or GLP-1 receptor agonists will not be allowed. Additionally, use of other basal insulins will not be allowed.

Investigators must use clinical judgment in the interest of safety of the patient at all times. In any situation that, in the investigator's opinion, may require an intervention that is not consistent with the requirements provided in this section, he or she should also consult the Lilly physician before such intervention is implemented, except when an immediate adjustment of the treatment regimen is medically required.

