	l	ening ad in										Treat	ment	Perio	d									Safety F/U
Visit	1	2	3ª	4	5	6	7	8	9	10	11	12	13	14	15	16	17	18	19	20	21	22	ETb	801
Week of Treatment	-3	-2	0	1	2	3	4	5	6	7	8	10	12	14	15	16	20	23	24	32	39	40		4 weeks post end of Tx
Allowable Deviation (days) ^c	1	3	±7	±3	±3	±3	3 3	±3	±3	-	±3	±3	±3	±3	1	3 3	±3	-	±3	±7	1	±7		±7
Fasting Visit ^d			X		X		X				X		X			X	X		X			X	X	X
PK only Visit										X					X			X			X			
Telephone Visit						X		X				X		X										
Concomitant medications	X	X	X	X	X	X	X	X	X	x	x	X	X	X	X	X	X	X	X	X	X	x	x	X
Review hypoglycemic events collected in the diary			X	X	x	x	X	X	x		x	x	x	X		x	x		x	X		x	X	x
									P	atien	t Edu	cation												
Diabetes education ^{i,j}		X																						
BG meter, SMBG trainingi		X																						
Dispense BG meter/supplies, as needed		X	X	X	X		X		x		x		x			X	X		x	X				
Study drug injection training			X																					
Hand out diary, instruct in use ^j		X	X				X										X					x		
Remind patients about 7-point SMBG ^k		X																		X				

	l	udy iod I										Stud	ly Per	iod II										Study Period III
	l	ening ad in										Treat	ment	Perio	d									Safety F/U
Visit	1	2	3ª	4	5	6	7	8	9	10	11	12	13	14	15	16	17	18	19	20	21	22	ET ^b	801
Week of Treatment	-3	-2	0	1	2	3	4	5	6	7	8	10	12	14	15	16	20	23	24	32	39	40		4 weeks post end of Tx
Allowable Deviation (days) ^c	1	3	±7	±3	±3	±3	±3	3	±3	-	±3	±3	±3	±3	1	3	±3	1	±3	±7	1	±7		±7
Fasting Visit ^d			X		X		X				X		X			X	X		X			X	X	X
PK only Visit										X					X			X			X			
Telephone Visit						X		X				X		X										
Review 7-point SMBG values collected in the diary			X																			x		
Dispense study drug			X	X	X		X		X		X		X			X	X		X	X				
Observe patient administer study drug ¹			x																					
Patient returns study drugs and injection supplies				X	X		X		X		X		X			X	X		X	X		x	X	
Assess study drug compliance				X	X	X	X	X	X		X	X	X	X		X	X		X	X		x	X	
Review insulin dose and adjustment per TTT algorithm			X	X	x	X	X	X	X		X	X	X	X		X	X		X	x				
Assess compliance with insulin dose adjustment TTT algorithm ^m				x	х		X		x		x		x			X	х		x	x		x	x	
									Ι	abora	ntory	Tests												
Serum pregnancy test ⁿ	X																							

	I	udy iod I										Stud	ly Per	iod II										Study Period III
	ı	ening ad in		Treatment Period															Safety F/U					
Visit	1	2	3ª	4	5	6	7	8	9	10	11	12	13	14	15	16	17	18	19	20	21	22	ET ^b	801

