- Vital sign measurements should be taken before obtaining an ECG tracing and before collection of blood samples for laboratory testing, at visits where required. The participant should sit quietly for 5 minutes before vital sign measurements are taken. For each parameter, 2 measurements will be taken using the same arm; the recordings should be taken at least 1 minute apart. Blood pressure must be taken with an automated blood pressure machine.
- b Dilated fundoscopic exam will be performed by a qualified eye care professional (ophthalmologist or optometrist) for all patients between Visit 2 and Visit 3 to exclude patients with proliferative diabetic retinopathy and/or diabetic maculopathy (macular edema), or nonproliferative diabetic retinopathy that requires acute treatment. The results from this exam will be recorded on a specific retinopathy eCRF as a baseline measure of retinopathy. Follow up dilated fundoscopic exam should be performed when clinically indicated, and, the results recorded on the retinopathy eCRF.
- ⁱ Includes counseling on diet and exercise, management of hypoglycemia, etc.
- j All training should be repeated as needed to ensure patient compliance.
- Patient is required to collect two 7-point SMBGs on nonconsecutive days prior to the next visit. A 7-point SMBG consists of measurements before and 2 hours after each of 3 main meals within the same day and at bedtime. These SMBG profiles will be collected by the patient within 2 weeks prior to the assigned visits. If 7-point SMBG is not performed, then data from the most recent nonconsecutive 4-point SMBG profiles can be used. If more than two 7-point SMBG profiles are available, the two most recent nonconsecutive profiles should be used. Patients will be required to collect a daily fasting BG and a 4-point SMBG once weekly between Visit 2 and 3, twice weekly from Visits 3-7 (Weeks 0-4) followed by weekly for the remainder of the study.
- Patients should administer their first dose of study drug at the end of this visit, after other study procedures and randomization.
- m Assessment of the patient's compliance to the TTT algorithm will be collected in the eCRF at Visits 7, 9, 11, 13, 16, 19, and 22 for the period since the previous clinic visit.

- ⁿ A serum pregnancy test will be performed at Visit 1 for women of childbearing potential only.

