Patients should be instructed to contact the sites if any of the above situations occurred, in order to adjust the insulin glargine dose per the TTT algorithm. In addition, for patients with baseline HbA1c ≤8.0%, the insulin glargine dose will be decreased by 20% immediately after randomization, not later than 7 days after the first dose of study drug, and will then remain unchanged during the stabilization period to decrease the risk of hypoglycemia. The insulin glargine dose will remain unchanged if baseline HbA1c is >8.0%. If the baseline HbA1c value for a patient is not available within the first 7 days after randomization, the study site should immediately consult the responsible Lilly physician (not later than the date of Visit 4) to discuss if an adjustment in insulin dose would be appropriate based on the available clinical data for the patient.

In addition to the clinic visits, one telephone visit will be scheduled during this period (Visit 6, Week 3). At this visit, procedures will include

- assessments of SMBG,
- adjustment of insulin dose for safety reasons (hypoglycemia and/or severe hyperglycemia),
- study drug compliance (will be re-assessed at the office visit),
- hypoglycemic events,
- concomitant medications, and
- AEs.

The data obtained at these telephone visits will be entered into the case report forms (CRFs) at the next office visit.

Titration Period (End of Visit 7 through Visit 22 [Weeks 5 through 40])

Throughout the treatment period, patients will collect the following data in the patient diary to be reviewed at the next office visit:

- SMBG.
- insulin dose assessments,
- insulin doses administered,
- dates when study drug was administered, and
- hypoglycemic events.

For that purpose, at each visit, study diaries for the period after the previous office visit, will be collected, and instructions will be reviewed at each visit. Study drug and injection supplies will be returned per the Schedule of Activities (Section 2) and according to local requirements. New supplies will be dispensed as needed.

In addition to the clinic visits, 3 telephone visits will be scheduled during this period. At each of these visits, procedures will include

- assessments of SMBG,
- compliance with insulin titration algorithm,
- insulin dose,
- study drug compliance (will be re-assessed at the office visit),
- hypoglycemic events.
- concomitant medications, and
- AEs.

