The site personnel will instruct the patient, with the patient insulin dose adjustment from the patient diary and study-specific training materials provided to the study sites, when and how to assess whether an insulin dose adjustment is needed using the algorithm. The investigator or his or her designee is responsible to ensure that the insulin dose titration regimen used by study participants follows the same requirements defined in the TTT plan throughout the study. The patient is responsible for completing the insulin dose assessments and making the required dose adjustments (self-adjustment). Assessment of insulin doses per the TTT algorithm and administered insulin doses will be recorded by the patient in study period-specific diaries. Patients should be instructed to contact the study site if they are unable to decide on the appropriate dose adjustment at any time during the trial. Site personnel will verify at each office or telephone visit that the assessment(s) has been made and that the insulin adjustment was appropriate. If needed, they will propose further adjustments based upon their review of data collected since the previous visit. If assessments were not made or the algorithm was not correctly followed, patients will receive additional training and instructions.

During the lead-in period (Visits 2 and 3 [baseline]), insulin doses should be adjusted per TTT algorithm (Table GPGI.3) only when needed to protect the safety of patients (occurrence of hypoglycemia or severe persistent hyperglycemia). See Section 5.1 for more details. Insulin dose assessments during this period will occur once per week.

During the treatment period, office visits will occur weekly or every other week during the first 2 months, and thereafter every 4 to 8 weeks to enable the site to properly monitor patients' usage of the TTT algorithm. After randomization, during the 4-week stabilization period, the insulin

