All patients who complete the treatment period are required to complete Visit 801, a safety follow-up visit, approximately 4 weeks after their last visit. Patients discontinuing the study early and performing an early termination (ET) visit will also be asked to perform the safety follow-up visit, so that the safety follow-up visit will be their last visit. During the safety follow-up period, patients will not receive study drug. Initiation of new antihyperglycemic therapy for the safety follow-up period will not be classified as “rescue therapy.”

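### Rescue criterion (c) has no scheduled diary review before treatment ends, so rescue starts may understate severe, persistent hyperglycemia after Week 32

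*Protocol*

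**What the plan says.** Protocol 9.2.2.2 states that severe, persistent hyperglycemia is to be collected so that the risk of extreme loss of control can be assessed. It sets three thresholds on the average of the once-weekly 4-point home profile: (a) above 270 mg/dL in Weeks 16 to 24; (b) above 240 mg/dL "over a consecutive 2-week period at any time 25 to 32 weeks post randomization"; and (c) above 200 mg/dL "over a consecutive 2-week period at any time beyond the first 32 weeks post randomization". Criterion (d) uses HbA1c at Week 24.

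On how the profiles reach the site, Protocol 5.1 (Titration Period) says that "patients will collect the following data in the patient diary to be reviewed at the next office visit". Home glucose values are first on that list. Protocol 7.1.3 gives the visit spacing: "office visits will occur weekly or every other week during the first 2 months, and thereafter every 4 to 8 weeks".

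For the stabilization period, 5.1 names mean profiles above 270 mg/dL among its triggers for a call: "Patients should be instructed to contact the sites if any of the above situations occurred". The lead-in text has a similar instruction. For the titration period, the contact wording concerns difficulty with study drug or with the titration algorithm.

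On what counts, SAP 5.1 (and Protocol 5.1) says: "Initiation of new antihyperglycemic therapy for the safety follow-up period will not be classified as" rescue therapy. SAP 6.13.2.2 plans a summary of rescue starts, a time-to-first-rescue model censored at the end of the treatment period, and a listing of patients who started rescue. It plans no count of patients who met a criterion.

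**The concern.** A prespecified criterion needs some scheduled point at which it can be found to be met. For (c), the data accumulate at home after Week 32, and the next planned look at them is the visit at which treatment ends. From then on, new therapy no longer counts as rescue.

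This matters for interpretation. Rescue starts are a stated safety endpoint and the only planned output for severe, persistent hyperglycemia. A low count after Week 32 could mean that control was good or that nobody was looking, and the planned tables cannot separate the two. A patient could also stay above one of the protocol's own thresholds for some weeks before any scheduled review.

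**Working it through.** The plan states no figure for this, so the check is one of timing.

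**Inputs, from the Schedule of Activities (Protocol Table GPGI.1)**
- Office visits from Week 16 on: Weeks 16, 20, 24, 32 and 40 (Visits 16, 17, 19, 20 and 22). All five carry the diary-review mark (the row for hypoglycemic events in the diary).
- PK-only visits from Week 16 on: Weeks 23 and 39 (Visits 18 and 21). Neither has a diary or insulin-review mark.
- Telephone visits: Weeks 3, 5, 10 and 14.
- HbA1c and fasting serum glucose: Weeks 24 and 40, with no sample at Week 32 or 39. No laboratory value fills the gap.

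**Method.** Assume one profile per week, and treat a criterion as met when two consecutive weekly profiles inside its window exceed the threshold. Wait = week of the next diary-review visit minus the week in which the pair is complete.

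| Criterion | Profiles in window | Pairs | Pair complete at | Next review | Wait (weeks) | Reviewed before Visit 22 |
|---|---|---|---|---|---|---|
| (a) | Weeks 16–24: 9 | 8 | Weeks 17–24 | Week 20 or 24 | 0 to 3 | 8 of 8 |
| (b) | Weeks 25–32: 8 | 7 | Weeks 26–32 | Week 32 | 32 − 32 = 0 to 32 − 26 = 6 | 7 of 7 |
| (c) | Weeks 33–40: 8 | 7 | Weeks 34–40 | Week 40 | 40 − 40 = 0 to 40 − 34 = 6 | 0 of 7 |

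**Share of the rescue window.** Criteria apply from Week 16 to Week 40, which is 40 − 16 = 24 weeks. The part after Week 24 is 16/24 = 67% and has one review before Visit 22. The part after Week 32 is 8/24 = 33% and has none. These are shares of calendar time, not of patients or events.

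**Variations**
- Visit 20 held 7 days late (Week 33): the first (c) pair is complete at Week 34, so still 0 of 7.
- The Week 32 profile also counted under (c), with Visit 20 at Week 33: one pair (Weeks 32 and 33) could be seen.
- Diaries looked at during Visit 21: 6 of 7 pairs would be seen, with 40 − 39 = 1 week of treatment left.
- Visit 22 extended to Week 44 (Protocol Appendix 8): the gap grows to 44 − 32 = 12 weeks, and still no (c) pair is reviewed before Visit 22.

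The Week 32 review cannot stand in for (c). A patient averaging between 200 and 240 mg/dL at that visit does not meet (b), and first meets (c) when the Week 34 profile is complete.

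**The case against.** The strongest reply is that the endpoint is the start of rescue, not the meeting of a criterion. Concomitant medications are recorded at every visit, Visit 21 included, so a start is captured whenever it happens. That stands. A reader might infer that rescue incidence itself is under-ascertained. The documents do not support this: a patient who meets (c) and is never rescued is not a missed endpoint event, but a case of the underlying condition that the endpoint does not show.

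A reader might also infer that (c) cannot operate at all. That is too strong. Patients may call if unable to decide on a dose (7.1.3), the investigator may ask for additional assessments (5.1), investigators are trained on the criteria and must use clinical judgment throughout (9.2.2.2), and 5.1 speaks of collecting diaries at each visit. Diary text and site training materials are not among the documents, so a contact instruction there cannot be ruled out. These routes are real, but none is a scheduled review.

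Two further inferences fail for want of figures. One is that the loss falls mainly on the worst-controlled arm and shrinks the difference in rescue. No rate of meeting (c) is given for any arm, so direction and size are both unknown. The other is bias in the estimands. The treatment-regimen analysis uses data regardless of rescue, and SAP 6.12.1.3 defines retrieved dropouts by study-drug discontinuation alone. For the efficacy estimand, a rescue that never starts means fewer data are excluded, but no bias is demonstrated.

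It is also fair to say that visits up to 8 weeks apart are a stated design choice, that patients self-titrate insulin weekly on fasting values to Week 40, and that (d) screens by HbA1c at Week 24. These reduce the number likely to reach (c), but they do not provide a way to find those who do.

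**Conclusion.** The point holds in a limited form. No scheduled diary review falls between Week 32 and the end of treatment, so (c) depends on unscheduled contact: 0 of 7 nominal profile pairs are reviewed before Visit 22. Criterion (b) is delayed by 0 to 6 weeks and not lost, since all 7 pairs are reviewed at Week 32 with 8 treatment weeks left.

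The count of rescue starts may therefore understate severe, persistent hyperglycemia in the last 8 of the 24 weeks, although 9.2.2.2 says the condition is to be collected. The number of patients affected and any imbalance between arms are unknown. The result rests on nominal visit weeks, one profile per week, and reading Visit 21 as the Schedule of Activities marks it. It does not touch the primary analysis. It is a gap in detection and reporting that is cheap to close.

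**What to change.** 1. Reconcile Protocol 9.2.2.2 with 5.1 and the Schedule of Activities, so that it is clear how (b) and (c) are identified when met, without changing any threshold or treatment. The means of identification is for the sponsor and investigators to decide.
2. At the existing diary-review visits (16, 17, 19, 20 and 22), record whether any 9.2.2.2 criterion was met since the last review (yes/no, with date). Including Visit 22 means that profiles meeting (c) after Week 32 are at least reported.
3. In SAP 6.13.2.2, add a table by arm giving the number of patients who met a criterion beside the number who started rescue.

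The cost is one eCRF item and one extra table. No new visit is needed, and the definition of the rescue endpoint stays as it is.
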